10.2. Secondary Efficacy Endpoints

The following secondary efficacy endpoints for the study will be summarized for the all treated population:

- Number, type and duration of infections other than acute SBIs
- Total serum IgG trough levels
- Episodes of fever ($\geq 100.4^{\circ}\text{C}$)
- Number of days out of work/school/kindergarten/day care or unable to perform normal daily activities due to infection
- Number of days of hospitalization due to infection
- Number of days of antibiotic use for infection prophylaxis and/or treatment

Data listings will also be provided.

Additionally, efficacy endpoints measured during both the CP Treatment Period and the IMP Treatment Period will be summarized side-by-side using the appropriate descriptive statistics using all treated population. For the CP Treatment Period, the summary descriptive statistics will be aggregated over all commercially licensed products.

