2.3.5 Pharmacokinetic Objectives

The PK objectives are:

- To determine the steady state serum concentrations of total IgG;
- To determine the PK profiles for total IgG following administration of the IMP.

3 Study Plan

This is a pivotal phase 3, open-label, single-arm, multinational, multicenter study to assess the tolerability, safety, efficacy, and pharmacokinetics of the IMP in adults and children with PIDD. The study will be conducted at up to 20 sites in the United States and Russia. All subjects will be treated on an outpatient basis with ProMetic BioTherapeutics Immune Globulin Intravenous Solution 10% (the IMP) for approximately 1 year.

A total of approximately 75 subjects aged 2-80 years will be enrolled in the study: approximately 50 subjects aged 17-80 years (Cohort 1) and approximately 25 children aged 2 to <17 years (Cohort 2). Only subjects 18 years of age and older and treated with commercially licensed immune globulin product will be enrolled by Russian sites, in accordance with Russian national legislation.

This is an open-label study; no subject or study personnel will be blinded.

A subset of subjects will be asked to participate in a PK sub-study (Section 6.13). Subjects who consent to participate in the PK sub-study will undergo a series of blood draws to assess the PK profile of the IMP before and after Infusion 6 (21-day cycle subjects) or Infusion 5 (28-day cycle subjects).

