6.2 Subject Diary

To obtain some of the data for evaluation of secondary endpoints, each subject (or parent/guardian, as appropriate) will be asked to fill in a diary throughout the study. The diary will be given to the subject at the baseline visit (Infusion 1 IMP/CP), along with instructions on how to complete it. The subject will be asked to record the following information in the diary from the first study visit until the LTSV:

- Any episode of fever ($\geq 100.4^{\circ}\text{F}$) measured at home with a thermometer provided by the study staff
- The number of days out of work/school/kindergarten/day care or unable to perform normal activities due to the underlying PIDD
- Date and duration of any hospitalizations (in case hospitalization is not at the site/location where the subject is being treated in the study)
- Any antibiotic treatments or other medications and the number of separate occasions they are taken during the study period
- Any other changes in medical history

Each time a subject returns to the study site, the Subject Diary will be reviewed for completeness and accuracy. Any discrepancies, especially from the phone call documentation up to 72 hours will be corrected by the subject at each visit, as necessary. Staff will review concomitant medications, AEs, and other safety information contained on the Subject Diary prior to administering CP or IMP. In addition, any other safety information (for example, laboratory results from prior visits) will also be reviewed prior to administration of CP or IMP. The diary will be returned to the subject at each visit with instructions to complete the diary and return with the diary at the next visit. Thermometers will be replaced only if lost or not functioning.

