2.2. Secondary Objectives

The secondary efficacy variables for this study are to examine to effects of IMP on the following:

- Serum total immunoglobulin G (IgG) trough concentrations obtained prior to each IMP infusion;
- Number of episodes of fever ($\geq 100.4^{\circ}\text{F}$);
- Number of days out of work/school/kindergarten/day care or unable to perform normal daily activities due to infections;
- Number of days of hospitalization due to infections;
- Number of days of antibiotics use for infection prophylaxis and/or treatment;
- Incidence of infections other than acute SBIs.

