11.10. Subject Diary

Subject diary data will be used to derive the following secondary efficacy endpoints:

- Episodes of fever ($\geq 100.4^{\circ}\text{C}$)

- Number of days out of work/school/kindergarten/day care or unable to perform normal daily activities due to infection
- Number of days of hospitalization due to infection
- Number of days of antibiotic use for infection prophylaxis and/or treatment

The subject diary data will be tabulated and listed.

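### SAP 10.2 and 11.10 set the fever threshold at 100.4°C, which no subject can reach, where SAP 2.2 and the protocol say 100.4°F

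*SAP*

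**What the plan says.** The SAP states the fever endpoint, which SAP 10.2 lists as "Episodes of fever", in three places, and the unit differs between them.

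- SAP 2.2 (Secondary Objectives) uses Fahrenheit: "Number of episodes of fever ($\geq 100.4^{\circ}\text{F".
- SAP 10.2 (Secondary Efficacy Endpoints) uses Celsius: "Episodes of fever ($\geq 100.4^{\circ}\text{C". Its list opens with "The following secondary efficacy endpoints for the study will be summarized for the all treated population", so this is the section that fixes what is tabulated and in which population.
- SAP 11.10 (Subject Diary) repeats the Celsius threshold under the opening words "Subject diary data will be used to derive the following secondary efficacy endpoints", so this is the section that fixes the data source.

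The protocol uses Fahrenheit wherever it states this endpoint: both synopsis lists (objectives and endpoints), Sections 2.3.3, 5.1.2 and 12.3.3, and the diary instruction in Section 6.2, which reads:

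- "Any episode of fever ($\geq 100.4^{\circ}\text{F}$) measured at home with a thermometer provided by the study staff"

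The fever question in the follow-up phone calls (Protocol 6.12.3.2) is also put in Fahrenheit.

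**The concern.** The Celsius unit stands in the two SAP sections that a programmer would work from, while the Fahrenheit unit stands in the SAP's list of objectives. The SAP therefore contradicts both itself and the protocol at the point where the derivation is specified. It does so in V2.0, the version revised for the final planned analyses.

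Two things are at stake. If the rule were applied as printed, the fever endpoint would be empty, and the side-by-side summary of the CP and IMP Treatment Periods promised in SAP 10.2 would show zero against zero. If analysts instead use Fahrenheit, as they presumably would, they depart from the written plan, and SAP Section 1 says that any deviation from the SAP will be described in the clinical study report. Correcting the unit avoids both.

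**Working it through.** **Inputs**

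- Threshold in SAP 10.2 and 11.10: 100.4°C.
- Threshold in SAP 2.2 and in Protocol 2.3.3, 5.1.2, 6.2 and 12.3.3: 100.4°F.
- The protocol's own equivalence, in the pneumonia footnote of Section 21.1: 38°C is given as 100.4°F.

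**Step 1: reproduce the protocol's equivalence.** With F = C × 9/5 + 32, 38 × 9/5 + 32 = 68.4 + 32 = 100.4°F. This agrees with Section 21.1.

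**Step 2: the threshold in the protocol's unit.** With C = (F − 32) × 5/9, (100.4 − 32) × 5/9 = 68.4 × 5/9 = 38.0°C. This is an ordinary definition of fever.

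**Step 3: the threshold as SAP 10.2 and 11.10 print it.** 100.4 × 9/5 + 32 = 180.72 + 32 = 212.72°F. This is above the boiling point of water, so no body temperature can meet it.

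**Step 4: consequence of the literal rule.** No recorded episode qualifies. The count is zero for every subject, hence zero in Cohort 1, in Cohort 2 and its age groups, and in the combined cohorts, in both the CP and IMP Treatment Periods.

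**Step 5: is this a text-reading artefact?** The same text shows Fahrenheit in SAP 2.2 and throughout the protocol's statements of the endpoint. Celsius appears only in SAP 10.2 and 11.10, and in both. A reading fault confined to those two places is unlikely.

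**The case against.** The strongest reply is that this is a recoverable slip. The number matches the protocol and only the unit letter is wrong. The printed value is impossible on its face, and SAP Section 1 says that the SAP supplements the protocol. All of this stands: the intended threshold is not in doubt.

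A second reply is that the threshold is already applied when the data are captured. Protocol 6.2 has subjects record episodes at 100.4°F or above with a supplied thermometer, and SAP 11.10 derives the endpoint from that diary. If episodes are counted as recorded, without re-applying a cut-off, nothing is lost. This also stands. The documents describe no separate series of home temperatures to which a programmer would later apply the SAP figure.

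A third reply is that nothing inferential depends on the endpoint. The protocol synopsis says that no hypotheses are tested on secondary efficacy endpoints, and Protocol 12.3.3 makes their analysis descriptive. This stands too.

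None of these replies makes the printed threshold correct. They limit the consequence, not the error.

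A reader might go further. Sites are planned in the United States and Russia (Protocol Section 3), and the SAP has no unit-conversion rule. One might therefore infer that temperatures recorded in Celsius would be compared with a bare 100.4, and that fevers at Russian sites would be lost unnoticed. The documents do not support this. Nowhere do they say that a site records the fever endpoint in Celsius. The thermometer is supplied by the study, although its unit is not stated, and the diary threshold is in Fahrenheit. Nor would a loss be hidden: SAP 10.2 promises data listings and SAP 11.10 promises that diary data are listed as well as tabulated, so recorded episodes would be visible beside an all-zero table.

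**Conclusion.** The point holds as a wrong threshold in the two operative SAP sections: 100.4°C (212.7°F) in place of 100.4°F (38.0°C).

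On a literal reading the effect is complete, with zero fever episodes in every subject and both periods. That is what the text prescribes, not a forecast of what the analysis will show. The likely practical effect is small, and it is nil if diary episodes are counted as recorded or if the programmer follows the protocol's unit.

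The error reaches one descriptive secondary endpoint. It does not touch the serious bacterial infection analysis, the sample size or the infusion safety target. The finding rests only on the printed units and an exact conversion; it needs no assumption about site practice.

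**What to change.** In SAP 10.2 and SAP 11.10, replace the Celsius threshold with ≥100.4°F (38.0°C), to match Protocol 5.1.2, 6.2 and 12.3.3 and SAP 2.2.

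The cost is a two-line correction. No endpoint changes and no data need to be collected again. If the SAP can no longer be amended, the clinical study report should state that the protocol's Fahrenheit threshold was used.

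A sentence saying that any temperature recorded in Celsius is converted before the threshold is applied would be optional clarification. The documents do not show that it is needed.

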11. EVALUATION OF SAFETY PARAMETERS

Evaluation of safety includes the analysis of treatment-emergent adverse events (TEAEs) and the analysis of laboratory investigations.

All TEAEs experienced will be recorded during the study and coded using the Medical Dictionary for Regulatory Activities (MedDRA) version 17.0. Details to be collected include TEAE diagnosis, date and time of onset and resolution, whether the event is ongoing, whether the event is serious, frequency, severity, outcome status, action taken and relationship to study drug (IMP or CP).

Safety endpoints measured during both the CP Treatment Period and the IMP Treatment Period will be summarized side-by-side using the appropriate descriptive statistics.

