5.2 Safety Endpoints

Safety will be evaluated via the following assessments:

- All reported AEs
- Rate (per subject per infusion), severity, and relatedness of AEs
- Frequency of temporally associated AEs
- Infusional AEs
- Assessment of local tolerability to IMP infusions: Reactions at infusion site
- Adverse reactions/suspected adverse reactions
- Vital sign changes, including changes in systolic and diastolic blood pressure, heart rate, respiratory rate, and body temperature
- Changes from Screening in physical examination findings
- Changes from Baseline in laboratory parameters (blood chemistry, hematology, urinalysis, hemolysis, d-dimer, protein S, and protein C concentrations, titers of antibodies to $\beta 2\text{GPI}$ and $\beta 2\text{GPI-DI}$)
- Frequency of clinical signs of hemolysis and/or thrombosis within 72 hours after infusion of the IMP
- IGIV-associated hemolysis
- Changes from Screening in viral safety markers (HAV, HBV, HCV, HIV-1, HIV-2, and B19)
- Comparisons of safety variables during treatment with IMP and during the Waiting Period on commercial product will be made as described in Section 12.3.4.

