12.3 Statistical Analysis Plan

12.3.1 Descriptive analyses

Continuous variables will be summarized using a standard set of descriptive statistics, consisting of frequency count, mean, standard deviation, median, maximum, and minimum. Time to event endpoints will be presented using Kaplan-Meier plots. Binary endpoints and categorical data will be summarized by count and percentage. Count data will be summarized by total counts and rates per subject per infusion.

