12.3.4 Safety Endpoints

Evaluation of safety includes the analyses of laboratory investigations, adverse events, and adverse reactions/suspected adverse reactions. No formal statistical analyses will be done comparing any of the safety endpoints between the Waiting Period on commercial product and the IMP treatment period. However, all safety endpoints measured during both the Waiting Period on commercial product and the IMP treatment period will be summarized side-by-side using the appropriate descriptive statistics. For the Waiting Period on commercial product, the summary descriptive statistics will be aggregated over all commercially licensed products.

Laboratory Data:

A summary by treatment period (Waiting period, IMP treatment period) will be produced for each of the laboratory parameters at each visit. These safety summaries will include descriptive summary tables and the data will be summarized in the form of frequency count, mean, standard deviation, median, minimum and maximum by treatment period and visit.

Adverse Events:

The seriousness, severity and relationship to the study drug of adverse events (AEs) will be observed and recorded on repeated administrations of the study drug using the MedDRA dictionary for the coding of AEs and serious adverse events (SAEs).

The number and proportion of subjects who have one or more AEs will be tabulated by seriousness, severity, and relationship to treatment according to body system and treatment period. Temporally related AEs will be similarly summarized. Rates of AEs will be estimated on a per infusion per subject basis and tabulated by seriousness, severity, and relationship to treatment according to body system and treatment period.

The following observations will be summarized, using the standard set of summary statistics (see 12.3.1).

- The number of infusions administered

- The total number of AEs experienced (irrespective of causality)
- The total number of AEs temporally associated with infusions
- During the infusion
- Within 1 hour after the infusion
- Within 24 hours after the infusion
- Within 72 hours after the infusion
- The number and proportion of infusions with which one or more infusional AEs are associated
- The number of infusional AEs per infusion
- Rate-related AEs

AEs will also be tabulated for the 30 subjects who received the highest doses of IMP and commercial product.

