6. STATISTICAL ANALYSES

6.1. General Considerations

Descriptive statistics and analyses will be provided by cohort, the age groups within Cohort 2 and, where appropriate, overall (combined all cohorts). Descriptive statistics for continuous variables will include the number of observations, mean, standard deviation (SD), median, minimum, and maximum values. For categorical variables, summary measures will include the number and percentage of subjects in each category.

Individual subject data will be presented in listings by cohort, subject identification number (ID), treatment schedule and, where appropriate, assessment.

All data summaries and tabulations will be prepared by using SAS® Version 9.1 or later.

For the purpose of reporting, subject weights and doses are rounded to zero decimal place.

Safety analyses will be summarized by the CP Treatment Period and by IMP Treatment Period.

Unless specifies otherwise, the efficacy analyses will be presented for all subjects in the all treated population as follows:

- Cohort 1 only
- Cohort 2 only
- Each of the 3 age groups within Cohort 2
- Cohorts 1 and 2 combined

The primary efficacy analysis will be based on the separate analyses for Cohort 1 for adult population and Cohort 2 for pediatric population using all treated population.

Efficacy data will be summarized similarly for CP Treatment Period.

PK analyses will be summarized by 21- or 28-day cycles for the IMP Treatment Period, unless otherwise specified.

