11.2. Treatment-Emergent Adverse Events

An overall summary table of TEAEs, including subjects experiencing at least one TEAE, at least one TEAE related to study drug, at least one TAAE, at least one infusional TEAE, at least one adverse reaction, at least one TEAE leading to study discontinuation, and at least one TEAE leading to death will be presented.

TEAEs including TAAEs, infusional TEAEs, and adverse reactions will be summarized by SOC and PT, showing the number and percentage of subjects experiencing a given event. In addition, TEAEs and TAAEs will be summarized by SOC, PT and worst severity; TEAEs will also be summarized by SOC, PT and relationship to study drug.

TESAEs will be similarly summarized. The number and proportion of subjects who have one or more TESAEs, and who have one or more serious TAAEs, will be presented. TEAEs will also be tabulated for the minimum of 30 subjects who received the highest average dose of IMP.

A subject will be counted only once for each preferred term when multiple AEs are coded to the same preferred term. If a subject experiences multiple AEs coded to the same preferred term, the maximum toxicity grade will be used for the summary.

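### SAP 11.2 omits the per-infusion AE rates that the protocol requires, so unequal CP and IMP exposure can by itself separate the side-by-side safety columns

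*SAP*

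**What the plan says.** **Protocol.** Section 5.2 lists as a safety endpoint "Rate (per subject per infusion), severity, and relatedness of AEs". Section 12.3.1 sets a general rule: "Count data will be summarized by total counts and rates per subject per infusion". Section 12.3.4 applies it to adverse events: "Rates of AEs will be estimated on a per infusion per subject basis and tabulated by seriousness, severity, and relationship to treatment", broken down further by body system and treatment period. The synopsis repeats this.

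**SAP.** Section 6.1 says "Safety analyses will be summarized by the CP Treatment Period and by IMP Treatment Period", and section 11 adds: "Safety endpoints measured during both the CP Treatment Period and the IMP Treatment Period will be summarized side-by-side using the appropriate descriptive statistics". Section 11.2 tabulates TEAEs by system organ class and preferred term, "showing the number and percentage of subjects experiencing a given event". It adds TEAE tables by worst severity and by relationship, and treats treatment-emergent SAEs the same way. No event rate per infusion or per unit of time is specified there. The general statistics in SAP 6.1 cover continuous and categorical variables only, with no counterpart to the protocol's rule for counts.

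SAP 11.1 does keep per-infusion measures for temporally associated and infusional events: the proportion of infusions affected and the number of events per infusion. A sentence shortly before that list, however, refers only to IMP subjects in the safety population.

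For secondary efficacy, SAP 10.2 says "efficacy endpoints measured during both the CP Treatment Period and the IMP Treatment Period will be summarized side-by-side", without naming a statistic.

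**The concern.** The percentage of subjects with at least one event grows with the number of infusions over which they are observed. If one period is longer, its percentage is higher even when the two products behave identically. A rate per infusion does not have this property, and it is the measure the protocol prescribed.

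The study has a single arm, so the CP columns are the only reference within the trial for IMP safety. A reader comparing 14% with 49% would see a product difference where there may be only a difference in exposure. Rates by system organ class, severity or relationship cannot be recovered afterwards from subject percentages, even with total exposure known.

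**Working it through.** **Inputs**
- IMP infusions: 17 on the 21-day cycle and 13 on the 28-day cycle (footnote to Protocol Table 4).
- CP exposure: at least 3 cycles for subjects switched from IGSC or an investigational product (Protocol 3.2.1); 36 weeks for a Group 3 subject enrolled at the start, less for later enrollees (Protocol 3.5.1); possibly longer than shown if recruitment is slow (footnote to Protocol Table 3).
- Risk of an AE per infusion: the documents give no figure for all TEAEs. Protocol 10.2.1 gives about 5% of infusions or less for common temporally associated events. I take 5% as the central assumption, with 1%, 10% and 40% as a range, equal on CP and IMP.

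**Reproducing the plan's exposure figures**

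The first and last IMP infusions are 48 weeks apart, so 48/3 + 1 = 17 and 48/4 + 1 = 13, as stated. A 36-week wait plus 52 weeks is 88 weeks, as stated. A 36-week wait holds 36/3 = 12 or 36/4 = 9 CP infusions.

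**Subject percentages under equal risk**

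With risk p per infusion, k infusions and independence, the percentage with at least one AE is 1 − (1 − p)^k. For example, 1 − 0.95^3 = 14.3% and 1 − 0.95^13 = 48.7%.

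| Risk p | CP, 3 inf. | CP, 9 inf. | CP, 12 inf. | IMP, 13 inf. | IMP, 17 inf. |
|---|---|---|---|---|---|
| 1% | 3.0% | 8.6% | 11.4% | 12.2% | 15.7% |
| 5% | 14.3% | 37.0% | 46.0% | 48.7% | 58.2% |
| 10% | 27.1% | 61.3% | 71.8% | 74.6% | 83.3% |
| 40% | 78.4% | 99.0% | 99.8% | 99.9% | 100.0% |

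On the 28-day cycle compare 3 or 9 with 13; on the 21-day cycle compare 3 or 12 with 17. At 40% the percentages approach 100% and the gap closes for the longer wait.

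**Event counts under equal risk**

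Expected events per subject are k × p, so the IMP/CP ratio is the ratio of infusions. For a 36-week wait it is 13/9 = 1.44 or 17/12 = 1.42. For a 3-cycle wait it is 13/3 = 4.3 or 17/3 = 5.7.

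**Allowing for correlation within subjects**

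With a beta-binomial model at p = 5% and intra-subject correlation ρ, set a = p(1 − ρ)/ρ and b = (1 − p)(1 − ρ)/ρ. The probability of no AE in k infusions is Γ(b + k)Γ(a + b) / [Γ(b)Γ(a + b + k)].

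| ρ | 3 inf. | 9 inf. | 13 inf. | 17 inf. |
|---|---|---|---|---|
| 0.05 | 13.6% | 31.9% | 40.3% | 46.8% |
| 0.20 | 11.8% | 22.8% | 27.0% | 30.1% |

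The gap shrinks but remains.

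**The protocol's measure**

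Events divided by infusions gives k × p / k = p. At 5% that is 5.0 per 100 infusions in both periods, whatever their length.

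**The case against.** The strongest reply is that the SAP has not abandoned exposure. SAP 11.1 keeps per-infusion measures for temporally associated and infusional events and tests the percentage of affected infusions against 40%. SAP 10.1 annualizes the SBI rate as 52n/w with time on study as an offset, and SAP 6.1 says efficacy data will be summarized in a similar way for CP. SAP 9.1 reports infusions, weeks and years of exposure to IMP or CP, so a reader can see that the periods differ. No formal CP-IMP comparison is planned. SAP section 1 presents the SAP as a supplement to the protocol, so the protocol's rate is not expressly revoked.

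Much of this stands, and it rules out several stronger readings that a reader might infer:
- That the SAP contains no per-infusion rates. It does, for temporally associated and infusional events; only their application to CP is unclear.
- That SAP 10.2 commits to raw totals of days and episodes. It names no statistic, and Protocol 12.3.3 is equally general.
- That the two periods always differ greatly in length. A 36-week wait gives a ratio of only about 1.4, and the CP schedule runs to 13 infusions and may extend further.
- That a test or error rate is affected, or that the display would flatter IMP. No test is involved, and a shorter CP period works against IMP.

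The reply does not cover the tables of all TEAEs and treatment-emergent SAEs. SAP 11.2 names the statistic for them, it is not the one in Protocol 12.3.4, and exposure totals do not allow the missing rates to be rebuilt. A programmer working from the SAP would not produce them.

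**Conclusion.** The point holds for all TEAEs and treatment-emergent SAEs, including the severity and relationship tables. Protocol 12.3.4 requires per-infusion rates by treatment period, and SAP 11.2 specifies only subject counts and percentages.

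Under equal risk the spurious gap is large for a 3-cycle wait (14% versus 49% at 5% risk on a 28-day cycle) and moderate for a 36-week wait (37% versus 49%). These figures assume a constant risk per infusion, the same on both products, and independent infusions. The 1% to 40% range is illustrative, and the actual mix of waiting times is not given in the plan. The consequence is confined to descriptive interpretation of the only reference within the trial.

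For SAP 11.1 and 10.2 the finding is narrower: coverage of CP, and the denominator for side-by-side counts, are left unstated.

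**What to change.** - **SAP 11.2:** for each treatment period, add AE rates per infusion for all TEAEs and treatment-emergent SAEs, by system organ class, seriousness, severity and relationship, as Protocol 12.3.4 requires. Put total infusions and subject-years in each period's column header. Keep the subject percentages alongside.
- **SAP 11.1:** state that the per-infusion summaries of temporally associated and infusional events are produced for the CP period as well as for IMP.
- **SAP 10.2:** where counts of episodes and days are shown side by side, give them with an exposure denominator. This can be per infusion, following Protocol 12.3.1, or per subject-year, as SAP 10.1 already does for SBIs. The choice between the two is open; stating one is what matters.

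The cost is extra table columns. The exposure data are already summarized under SAP 9.1, so no new data collection is needed.
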